### **10.1.2 Double-blind randomized treatment period (Day 1 to Week 52)**

Upon successful completion of the Run-in phase, patients will be randomly allocated to either sotagliflozin 400 mg and glimepiride placebo, sotagliflozin 200 mg and glimepiride placebo, glimepiride and sotagliflozin placebo, or glimepiride placebo and sotagliflozin placebo for the double-blind Treatment Period lasting 52 weeks. All randomized patients will be followed at regular on-site visits for the duration of the Treatment Period.

[figure not shown]
At each on-site visit, the patient must return to the investigation site in the morning in fasting condition (at least 8 hours fasting) and holding antidiabetic drug(s).

In the event of abnormal urinalysis findings, urine cultures should be performed (microbial testing). Additionally, urine cultures should be performed if at any point the PI suspects the presence of a UTI.

#### **10.1.2.1 On-site randomization visit on Day 1 (Baseline; Week 0)**

The following procedures will be performed at this visit:

- Exclusion criteria are to be reviewed, including assessment of compliance during the Run-in phase.
- Concomitant medications are assessed.
- Measurement of body weight.
- Abbreviated physical examination including vital signs. After 5 minutes resting, seated SBP, DBP, and HR will be assessed 3 times with at least 1 minute between each measurement (see Appendix C for details).
- IMP accounting and compliance for single-blind placebo Run-in phase.
- IRT to be notified and randomization will occur.
- Diet and exercise instruction.
- Patient diary is collected/reviewed and a new one is dispensed. Instructions/training are provided as needed.
- Instruction on DKA symptoms and instruction on basic GU hygiene and hydration is provided (see Appendix B).
- Fasting SMBG is assessed.
- The following laboratory testing (by the central laboratory):
  - FPG
  - HbA1c
  - Urine pregnancy testing for WOCBP
  - Clinical chemistry (including amylase, lipase) and hematology
  - Fasting lipids

- Urinalysis (dipstick and microscopy)
- Additional laboratory testing at this visit:
  - 
  - 
- IMP is dispensed.
- AEs/SAEs/AESI/EOSI and hypoglycemia (if any) are reported.
- Patients are instructed to return to the site in the fasting state for Visit 4 (Week 2).
- For accountability and compliance purposes, patients are instructed to return to the site with their used, unused, and in-use wallet(s) dispensed during Visit 3.

#### **10.1.2.2 On-site visits at Weeks 2 to 39 (Visits 4 to 11)**

The following will be performed at these visits:

- Measurement of body weight.
- Abbreviated physical examination including vital signs (SBP, DBP, HR, and respiratory rate). After 5 minutes resting, seated SBP, DBP and HR will be assessed 3 times with at least 1 minute between each measurement (all visits except Visit 10, see Appendix C for details). At Visit 10 (Week 26), a complete physical examination will be performed (Section 9.2.1.4).
- Diet and exercise instruction (Visit 10 only).
- Instruction on DKA symptoms and basic GU hygiene and hydration (all visits except Visit 4; see Appendix B) is provided.
- IRT to be notified.
- Patient diary is collected/reviewed and a new one is dispensed. Instructions/training are provided as needed.
- IMP dispensed.
- IMP accounting and compliance.
- Concomitant medications are assessed.
- Fasting SMBG is assessed.
- 12-lead ECG (Visit 10 only).
- The following laboratory testing (by the central laboratory):
  - FPG (all visits except Visit 4)
  - HbA1c (Visit 7, 10, and 11)
  - Urine pregnancy testing for WOCBP
  - Clinical chemistry (including amylase, lipase, and hematology; Visits 7, 10, and 11)
  - Fasting lipids (Visit 10 only)

- Urinalysis (dipstick and microscopy; Visit 10 only)
- Additional laboratory testing at this visit:
  - [REDACTED]
- PQAT (Visit 10 only).
- AEs/SAEs/AESI/EOSI and hypoglycemia (if any) are reported.
- Patients are evaluated for glycemic rescue (see Section 9.1.5.6).
- Patients are instructed to return to the site in the fasting state for their next visit.
- For accountability and compliance purposes, patients are instructed to return to the site with their used, unused, and in-use wallet(s) at the next visit.

#### **10.1.2.3 Phone call visit at Week 15 (Visit 8)**

The following will be performed at this visit:

- Concomitant medications are assessed.
- Fasting SMBG is assessed.
- AEs/SAEs/AESI/EOSI and hypoglycemia (if any) are reported.
- Patients are evaluated for glycemic rescue (see Section 9.1.5.6).
- Patients are instructed to return to the site in the fasting state for their next visit (Visit 9).

#### **10.1.2.4 On-site Visit 12 (Week 52) or end of treatment**

The following will be performed at this visit:

- Measurement of body weight.
- Complete physical examination including vital signs (SBP and DBP, HR, and respiratory rate). After 5 minutes resting, seated SBP, DBP, and HR will be assessed 3 times with at least 1 minute between each measurement (see Appendix C for details).
- Diet and exercise instruction is provided.
- Instruction on DKA symptoms basic GU hygiene and hydration (see Appendix B) is provided.
- IMP accounting and compliance.
- Patient diary, including hypoglycemia log, is collected/reviewed.
- Concomitant medications are assessed.
- Fasting SMBG is assessed.
- 12-lead ECG.
- The following laboratory testing (by the central laboratory):
  - FPG

- HbA1c
- Clinical chemistry (including amylase, lipase) and hematology
- Fasting lipids
- Urine pregnancy testing for WOCBP
- Urinalysis (dipstick and microscopy)
- Additional laboratory testing at this visit:
  - [REDACTED]
- PQAT
- IRT to be notified.
- AEs/SAEs/AESI/EOSI and hypoglycemia (if any) are reported.
- A telephone call for last study visit (Visit 13) is scheduled in 2 weeks.

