### 6.1.2 Double-blind Treatment Period (Week 0 to Week 52)

Eligible patients will be randomized on Day 1 (Visit 3). In order to qualify for randomization, patients must demonstrate compliance during the single-blind placebo Run-in phase based upon tablet and capsule count ( $\geq 80\%$ ), and as assessed at the Investigator's discretion.

Randomization will be stratified by:

- HbA1c at Screening ( $\leq 8.5\%$ ,  $> 8.5\%$ )
- SBP at Screening ( $< 130$  mmHg,  $\geq 130$  mmHg)

Following randomization, patients will be treated in a double-blind manner for 52 weeks. A total of 930 patients  $\geq 18$  years of age (or  $\geq$  legal age of majority, whichever is greater) will be randomly assigned at a 2:1:2:1 ratio to the following 4 treatment groups on top of open-label metformin:

- Sotagliflozin 400 mg group: Sotagliflozin 400 mg, given as two 200 mg tablets and 2 glimepiride placebo capsules, taken orally once daily before the first meal of the day (N = 310 patients).
- Sotagliflozin 200 mg group: Sotagliflozin 200 mg, given as one 200 mg tablet and 1 sotagliflozin-matching placebo tablet, and 2 glimepiride placebo capsules, taken orally once daily before the first meal of the day (N = 155 patients).
- Glimepiride group: 2 sotagliflozin-matching placebo tablets, and combination of 2 glimepiride (or matching placebo) capsules with adequate dose strengths per dose titration (titrated up to 6 mg, see Table 2), taken orally once daily before the first meal of the day (N = 310 patients).
- Placebo group: 2 sotagliflozin-matching placebo tablets and 2 glimepiride placebo capsules, taken orally once daily before the first meal of the day (N = 155 patients).

Fasting glucose (plasma or serum) and HbA1c will be masked to study sites and patients after randomization until study end. Additionally, urinalysis by dipstick will not include the measurement of urine glucose.

All visits will be on-site with the exceptions of Visit 8 (Week 15) and Visit 13 (Week 54) which will be telephone visits.

If a patient discontinues with investigational medicinal product (IMP) early during the Treatment Period, the patient will have a Premature End of Treatment (EOT) Visit and a Follow-up phone call 2 weeks after the last dose of IMP. In addition, every effort will be made to have the patients return to the site at the time corresponding to their scheduled visits, particularly the Week 26 and Week 52 visits.

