### **10.1.3 Post-treatment follow-up period**

The post-treatment Follow-up period will include a Follow-up phone call 2 weeks after the last dose of IMP.

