#### **10.1.3.1 Follow-up phone call Visit 13 (Week 54)**

The following information will be discussed during this phone call:

- IRT notified for end of study.
- Concomitant medications are assessed. Post-treatment antihypertensive medication is added or adjusted as per instructions given in Section 8.9.
- SMBG is reviewed.
- AEs/SAEs/AESI/EOSI and hypoglycemia (if any) are reported.
- The patient is instructed to schedule future follow-up with their own personal physician.

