### **10.3.3 List of criteria for permanent treatment discontinuation**

Patients may withdraw from treatment with the IMP at any time for any reason or this may be the Investigator's decision. Patients should discuss stopping study medication with the site before doing so in order that questions can be addressed, glycemic therapy adjusted, and a follow-up assessment arranged. All efforts should be made to document the reasons for treatment discontinuation and this should be documented in the e-CRF.

The following reasons lead to permanent discontinuation:

- At the patient's own request (ie, withdrawal of consent for treatment).
- If, in the Investigator's opinion, continuation with the administration of the study treatment would be detrimental to the patient's well-being.
- Intercurrent condition that requires permanent discontinuation of the study treatment as long as the abnormality persists and if the casual relationship of the concerned event and the IMP is possible (according to the Investigator's best medical judgment).
- Pregnancy (in female patients).
- Specific request of the Sponsor.

Any abnormal laboratory value will be immediately rechecked to confirm the result before a decision is made to permanently discontinue IMP for the concerned patient.

For patients who prematurely discontinue the IMP, the assessments planned at the EOT visit (see Section 10.1.2.4) will be performed as soon as possible after treatment discontinuation. The reason(s) for IMP discontinuation will be clearly specified. This EOT assessment may occur at a regularly scheduled or unscheduled visit.

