#### **10.3.4 Handling of patients after permanent treatment discontinuation**

Every effort should be made to maintain patients in the study. Patients should be followed-up according to the study procedures specified in this protocol up to the scheduled date of study completion, or up to recovery or stabilization of any AE to be followed-up as specified in this protocol, whichever comes later.

If a patient decides to discontinue IMP early, a Premature EOT visit (see Section 10.1.2.4) should be scheduled prior to treatment discontinuation, if possible. If not possible, the Premature EOT visit should be scheduled as soon as possible after treatment discontinuation. For patients that discontinue treatment but remain in the study, remaining study visits should occur as scheduled where possible. The IRT should be notified of EOT.

After permanent treatment discontinuation, of the investigational products, any treatments (other than SGLT2 inhibitors) are permitted, as deemed necessary by the Investigator.

All confirmed cases of permanent treatment discontinuation should be recorded by the Investigator in the appropriate pages of the e-CRF.

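### The follow-up call two weeks after the last dose is scripted as the end of the study, with no exception for patients who stop study drug early but should stay to Week 52

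*Protocol*

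**What the plan says.** **Instructions that close the patient out**

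- Protocol 10.1.2.4 covers both the Week 52 visit and end of treatment. Its last item is "A telephone call for last study visit (Visit 13) is scheduled in 2 weeks", with no condition attached.
- Early stoppers are sent there twice. Section 10.3.3 says "the assessments planned at the EOT visit (see Section 10.1.2.4) will be performed as soon as possible after treatment discontinuation", and 10.3.4 says "a Premature EOT visit (see Section 10.1.2.4) should be scheduled prior to treatment discontinuation, if possible".
- Section 10.1.3 states: "The post-treatment Follow-up period will include a Follow-up phone call 2 weeks after the last dose of IMP". Flow chart note b and 6.1.3 apply that timing to every patient, and 6.1.3 names premature as well as scheduled stopping.
- Section 10.1.3.1, headed Visit 13 (Week 54), is the only script for the call. It includes "IRT notified for end of study" and "The patient is instructed to schedule future follow-up with their own personal physician".

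**Instructions that keep the patient in**

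- Section 6.1.2 gives an early stopper a premature end-of-treatment visit and a two-week call. It then adds that "every effort will be made to have the patients return to the site at the time corresponding to their scheduled visits", naming Weeks 26 and 52 in particular. The synopsis and flow chart note a say the same.
- Section 10.3 has the patient remain and be followed for the rest of the study.
- Section 10.3.4 says "For patients that discontinue treatment but remain in the study, remaining study visits should occur as scheduled where possible", and that the IRT is told of end of treatment.
- SAP 1.1 expects patients who stop treatment early to continue in the study.

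**The concern.** For a completer the two sets of instructions agree, because two weeks after the last dose is about Week 54 and that call really is the last contact. For an early stopper they conflict. The same call falls well before Week 52, yet the checklist names it the last study visit and its script registers end of study in the IRT. No text says that these items are withheld or deferred for someone who has stopped drug but not left the study.

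The affected data matter to the analysis. Protocol 11.4.2.1 and SAP 2.4.4 use values obtained after drug discontinuation. The SAP's primary imputation (2.4.4.1) is fitted within each treatment group, using only patients who stopped drug before the visit and still have the endpoint. An early stopper closed out in error becomes a patient to be imputed and is lost as a source for the imputation.

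**Working it through.** The point rests on cross-references and on no stated figure of the plan, so the check is to trace the text for one case.

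**A patient who stops drug at Week 20 (hypothetical)**

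| Step | Following 10.1.2.4 and 10.1.3.1 literally | Following 6.1.2, 10.3 and 10.3.4 |
|---|---|---|
| Premature end-of-treatment visit | Last study visit booked in 2 weeks | End-of-treatment assessments; IRT told of end of treatment |
| Call at Week 20 + 2 = 22 | IRT told of end of study | Safety call; patient remains in the study |
| Weeks 26, 39 and 52 | None expected after end of study | Visits as scheduled, with HbA1c at each |

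**Timing of Visit 13.** Flow chart note b and 6.1.3 count two weeks from the last dose, which is Week 22 here. Section 10.1 counts two weeks (±3 days) from Visit 12, which is about Week 54. Both cannot describe the same visit for this patient.

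**Which values are exposed.** Week 52 values are exposed for early stoppers generally. Week 26 values (HbA1c, weight) and Week 12 values (SBP) are exposed only for patients who stop before those visits. SAP 2.5.4 limits this further, because a premature end-of-treatment measurement can be re-allocated to a scheduled visit if it falls in the window: study days 70 to 104 for Week 12, 154 to 227 for Week 26, and 319 onward for Week 52. Inside the window the value is not missing, but a measurement near the last dose stands in for the later off-treatment one. Outside it, the value is missing.

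**Could this change the imputation method?** SAP 2.4.4.1 moves to the washout back-up if any group has fewer than 5 retrieved dropouts. Take a 155-patient group and assume a stopping rate d, with every stopper otherwise providing the endpoint. The share of stoppers that must be lost to leave 4 is 1 − 4/(155 × d):

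- d = 5%: 155 × 0.05 = 7.75; 1 − 4/7.75 = 48%
- d = 10%: 155 × 0.10 = 15.5; 1 − 4/15.5 = 74%
- d = 20%: 155 × 0.20 = 31; 1 − 4/31 = 87%

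The rates are assumptions, since the documents give no drug-stopping rate. A switch of method would need a large loss. A smaller loss would only thin the set of retrieved dropouts.

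**The case against.** The strongest reply is that the governing rule is clear. The synopsis, flow chart note a and 6.1.2 all list the two-week follow-up and then, in addition, the remaining scheduled visits, so they do not treat that call as the last contact. Section 6.1.2 also provides a telephone contact around the originally scheduled end of study for patients who decline site visits. Section 9.2.1.2 has safety data collected to scheduled study end. The close-out script carries a Week 54 label, 10.3.3 imports assessments rather than the booking of a call, and 10.3.4, written for these patients, has the IRT told of end of treatment.

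Most of this stands as evidence of intent, and it sets the limit of the point. It does not remove the conflict. Section 10.3.4 refers to the premature visit itself as 10.1.2.4. Even without the booking line, the call is still required two weeks after the last dose, and 10.1.3.1 is its only script. Telling the IRT of end of treatment at one visit does not cancel an end-of-study entry at the next contact.

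A reader might infer that the plan would lose the Week 26 and Week 52 data of early stoppers. The documents do not support that: loss requires a site or the IRT to follow the checklist against a repeated retention rule. Nor can the 30% dropout in the sample-size section be used to size the loss. It is an input to the completer power statement, and completers must also be free of rescue therapy (11.4.2.1), so it is not a drug-stopping rate. The SAP's hypoglycemia safety analyses (2.4.5.1) end one day after the last dose and would not be affected.

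**Conclusion.** The point holds as a conflict between operative instructions. The end-of-treatment checklist and the Visit 13 script, read with flow chart note b and 6.1.3, treat the call two weeks after the last dose as the end of the study for everyone. The retention rules keep early stoppers in to Week 52, and Visit 13 has two timings. The consequence is a risk from literal execution by a site or the IRT: fewer observed off-treatment values and fewer retrieved dropouts.

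The size of that risk cannot be estimated from the documents, which give neither a drug-stopping rate nor any indication of how the IRT handles the entry. No sample-size figure, hypothesis or analysis rule changes. The text is worth correcting because the rule as written is wrong for early stoppers, the data at risk feed the primary analysis, and the correction costs very little.

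**What to change.** Reconcile 10.1.2.4, 10.1.3 and 10.1.3.1 with 6.1.2, 10.1, 10.3 and 10.3.4:

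1. In 10.1.2.4, limit the last-study-visit (Visit 13) line to patients completing Week 52. For a premature end-of-treatment visit, describe the two-week call as a post-treatment safety call and have the site confirm the remaining scheduled visits.
2. In 10.1.3.1, state that the end-of-study IRT entry and the other close-out items belong to the patient's actual last study contact.
3. Give Visit 13 one timing, and give the early stopper's safety call its own label in flow chart note b and 6.1.3.

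No recommendation is made on when a patient should be directed to their own physician. That is for the sponsor to settle when reconciling the sections.

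The cost is a short protocol clarification and an IRT/e-CRF completion note. No visits are added, because 6.1.2 and 10.3.4 already call for them. SAP section 4 records that the database is locked, so new wording cannot alter data already collected. The tabulation of end-of-study status against end-of-treatment status already planned in SAP 2.2 can help show whether early stoppers were closed out.

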### **10.1.3 Post-treatment follow-up period**

The post-treatment Follow-up period will include a Follow-up phone call 2 weeks after the last dose of IMP.

#### **10.1.3.1 Follow-up phone call Visit 13 (Week 54)**

The following information will be discussed during this phone call:

- IRT notified for end of study.
- Concomitant medications are assessed. Post-treatment antihypertensive medication is added or adjusted as per instructions given in Section 8.9.
- SMBG is reviewed.
- AEs/SAEs/AESI/EOSI and hypoglycemia (if any) are reported.
- The patient is instructed to schedule future follow-up with their own personal physician.

## **10.2 DEFINITION OF SOURCE DATA**

### **10.2.1 Source data to be found in patient's file**

Evaluations recorded in the e-CRF must be supported by appropriately signed source documentation related but not limited to the following:

- Agreement and signature of ICF with the study identification.
- Study identification (name).
- Patient number, confirmation of randomization, treatment batch number, dates and doses of study medication administration.

- Medical, surgical, diabetes history, including information on:
  - Demography, inclusion and exclusion criteria
  - Last participation in a clinical trial
  - Contraception method for WOCBP
  - Previous and concomitant medication
- Dates and times of visits and assessments including examination results.
- Vital signs, height, body weight, laboratory reports, Investigation results (eg, ECG traces, imaging reports), spirometry reports.
- Adverse events and follow-up:
  - In case of SAE, the site should file in the source documents at least copies of the hospitalization reports and any relevant examination reports documenting the follow-up of the SAE
- Date of premature treatment discontinuation (if any) and reason.
- Date of premature study discontinuation (if any) and reason.
- Nursing notes.
- Dietician's notes.
- Physician's notes.
- Patient's diary.

#### **10.2.2 Source data verification requirements for screen failures**

For screen failure patients, the following source data must be verified: patient's identification details, the informed consent signed by the patient, the study identification (name), dates of study visits, and the main reasons for screen failure.

### **10.3 HANDLING OF PATIENT TEMPORARY OR PERMANENT TREATMENT DISCONTINUATION AND OF PATIENT STUDY DISCONTINUATION**

The IMP should be continued whenever possible. In case the IMP is stopped, it should be determined whether the stop can be made temporarily; permanent IMP discontinuation should be a last resort. Any IMP discontinuation should be fully documented in the e-CRF. In any case, the patient should remain in the study and followed for the remainder of the study duration to collect vital safety status and endpoint.

#### **10.3.1 Temporary treatment discontinuation with investigational medicinal product**

Temporary treatment discontinuation may be considered by the Investigator because of suspected AEs. Lower extremity complications (such as skin ulcers, infection, osteomyelitis and gangrene) requiring treatment should lead to temporary discontinuation of IMP. Reinitiating treatment with

the IMP will be done under close and appropriate clinical and/or laboratory monitoring once the Investigator has considered, according to his/her best medical judgment, that the occurrence of the concerned event was unlikely to be related to the IMP.

It is in the interest of the patient to monitor their blood glucose during the temporary discontinuation period, therefore regular determination of SMBG is to be performed and documented (see Section 9.2.1.6).

For all temporary treatment discontinuations, the duration should be recorded by the Investigator in the appropriate pages of the e-CRF when considered as confirmed.

Temporary treatment discontinuation, as decided by the Investigator, corresponds to more than 1 dose not administered to the patient.

Use of any other anti-hyperglycemic medication during the time of temporary treatment discontinuation (eg, insulin during a hospitalization) is recorded as concomitant medication with the name and doses recorded in the e-CRF.

